- End of study: At 48-weeks, participants will complete all study assessments. Participants will be provided additional study drug (6-months supply) for the period of time for go/no-go analysis.
- Early termination: In the event of early termination due participant withdrawal of consent or removal by the investigator from the trial, the 48-weeks/early termination visit should be completed in all possible cases, if the participant has been randomized to therapy or placebo. No new investigational product will be administered.
- Unscheduled visits: If needed, unscheduled visits can be performed at the discretion of the Site Principal Investigator. Unscheduled visits should include collection of adverse events, concomitant medications, brief neurological and physical examination, and clinical blood laboratories, if indicated.
- Go/no-go: At the completion of the go/no-go analyses, participants will complete an additional visit to assess safety and collect study medication (no-go) or to be enrolled in the 48-weeks extension study (go). In the event of a “go” decision, trial duration will be extended to 96-weeks. Participants will remain blinded to randomization and group assignment will be unchanged. A safety visit will be performed at 74-weeks. The end of study visit will be performed at 96-weeks, and will include the co-primary outcome measures of the ADAS-cog13 and the ADCS-ADL-MCI, as well as the CDR-SB, neurological and physical exams, blood laboratories, assessment of adverse events, MRI, and lumbar puncture for CSF protein analysis.

9.2.2. Safety assessments. Participants will undergo brief physical and neurological examinations, laboratory testing, and EKG at all follow-up visits (12, 24, and 48-weeks /early termination). Adverse events will be assessed by the study site clinician. Adverse events include signs or symptoms that may or may not be related to study medication, abnormalities detected during physical examination, or clinically significant laboratory abnormalities. The Columbia Suicidality Severity Rating Scale (C-SSRS) will be performed at the baseline, 24-week, and 48-week visits. Adverse events will be graded as mild, moderate, or severe according to section 13.1.1, and recorded on case report forms. Regular safety reports will be prepared by the ADCS and submitted to an independent Data and Safety Monitoring Board (see section 13.3.3).

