4 PARTICIPANT POPULATIONS

4.1 Population Definitions

The following populations will be evaluated and used for presentation and analysis of the data:

- **Enrolled Participants:** Participants who signed an informed consent form and were assigned a Participant Identification number (PID)
- **Intent to Treat (ITT) Population:** All enrolled participants who received a randomized treatment assignment.
- **Safety Population:** Enrolled and randomized participants who received at least 1 dose of blinded study therapy (nicotinamide or placebo). This will be the primary analysis population used for the safety analyses.
- **Modified Intent-to-Treat (mITT) population:** All randomized participants who have a baseline assessment of the endpoint, and who have at least one evaluation of the endpoint following baseline.

- **Per-protocol population:** All randomized participants who completed trial activity through week 48 including lumbar puncture.

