5.2 Analysis of Safety Outcomes

Safety analyses will be conducted on the Safety Population.

The safety and tolerability of high-dose nicotinamide treatment in individuals with MCI due to AD or mild AD dementia will be assessed by the following, for each arm separately:

- Treatment emergent Adverse Events (TEAEs) summarized:
 - Overall and by number of subjects with an AE
 - By severity and relation to investigational product

- By number of events and by subjects with an event by System Organ Class (SOC)
- By Preferred Term (PT) within SOC
- Serious adverse events (SAEs) including deaths summarized as for TEAEs
- Vital signs (weight, BMI, blood pressure, pulse) will be presented with means and standard errors at each study visit
- Descriptive statistics for ECG interval data will also be reported across visits including baseline, week 24 and week 48 or early termination.
 - Proportion of subjects with at least 1 abnormal ECG by treatment arm
 - Proportion of subjects with at least 1 abnormal QTC by treatment arm
 - The QTC will be computed using the Friderica formula. Abnormal will be defined as above 460 for men and above 470 for women.
 - Average within subject change in QTC by treatment arm (baseline to latest available)
- Adverse events (AEs) leading to discontinuation

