5.5.2 Early Termination

Early termination from the study includes participants who leave the study and/or discontinue treatment prior to completing the week 48 visit. Proportions of participants who prematurely discontinued the study prior to the week 48 visit will be compared between the study arms.

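### SAP 5.2 measures QTc change to the last recorded ECG with no on-treatment limit, so a tracing taken after stopping can replace an on-drug one

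*SAP*

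**What the plan says.** SAP 5.2 plans one change-from-baseline ECG summary: "Average within subject change in QTC by treatment arm (baseline to latest available". No window around dosing is given. The Safety Population in SAP 4.1 is "Enrolled and randomized participants who received at least 1 dose of blinded study therapy (nicotinamide or placebo", so people who stop early are included.

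SAP 5.2 also plans:
- "Descriptive statistics for ECG interval data will also be reported across visits including baseline, week 24 and week 48 or early termination";
- how many people in each arm ever have an abnormal QTc, meaning above 460 for men and 470 for women;
- the proportion with any abnormal ECG, and a summary of adverse events that led to discontinuation.

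On stopping, Protocol 9.2.1 says that after consent withdrawal or removal by the investigator "the 48-weeks/early termination visit should be completed in all possible cases", and adds "No new investigational product will be administered". It sets no limit on the time since the last dose. SAP 5.5.2 allows stopping treatment and leaving the study to be separate events: "Early termination from the study includes participants who leave the study and/or discontinue treatment prior to completing the week 48 visit".

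The ECG schedule is inconsistent. Protocol 9.2.2 has "laboratory testing, and EKG at all follow-up visits (12, 24, and 48-weeks /early termination", and Protocol 9.2.1 also lists an EKG at week 12. Appendix 1 and SAP 3.1 show none between screening or baseline and week 24.

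**The concern.** ECG abnormality is a named measure under Primary Objective 2 (SAP 2.1). A change summary meant to show what the drug does to QTc should compare a pre-dose tracing with one taken during dosing. A rule that takes whichever ECG came last does not ensure that. When the last ECG follows discontinuation, it can displace an earlier tracing that was taken on drug.

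Elsewhere the SAP does restrict to treatment: adverse events are treatment-emergent (SAP 5.2), and the suicidality outcome counts responses given during treatment (SAP 5.2.1). QTc change has no matching limit. If a QTc effect wears off after stopping, the arm mean is pulled toward zero, and more so if those who stop had the larger effects. With about 24 people per arm, a few participants can move the mean.

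**Working it through.** **Inputs from the documents.** 47 randomised 1:1 (SAP 3.1), so about 24 per arm. Scheduled ECGs are as set out above. The documents give no QTc effect, no SD of QTc change, and no rate of people who stop drug and are then seen off drug. There is therefore no plan figure to reproduce, and every millisecond figure below is an illustration.

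**Step 1: who is affected.**
- Stops after week 24 and attends early termination off drug: the on-drug week-24 ECG is replaced. This is the case at issue.
- Stops after week 24, with the early-termination ECG taken at or near the last dose: no dilution.
- Stops after week 24 and is lost without that visit: week 24 is the latest ECG, so no dilution.
- Stops before week 24: under Appendix 1 and SAP 3.1 no earlier post-baseline ECG is scheduled, so none is replaced, though an off-drug early-termination ECG still enters the mean. If the week-12 EKG in Protocol 9.2.1 and 9.2.2 was done, that tracing would be replaced.

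**Step 2: uniform effect.** Let D be the on-drug shift and p the share of the arm whose latest ECG is off drug with the effect fully reversed. Reported mean = D × (1 − p). With D assumed to be 10 ms:

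| p (assumed) | Reported mean |
|---|---|
| 0 | 10.0 ms |
| 5% | 9.5 ms |
| 10% | 9.0 ms |
| 20% | 8.0 ms |
| 30% | 7.0 ms |

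**Step 3: larger effect in those who stop.** Assume 30 ms in them and 10 ms in the rest. On-drug mean = (1 − p) × 10 + p × 30; reported mean = (1 − p) × 10.
- p = 5%: 9.5 against 11.0 ms, an understatement of 13.6%.
- p = 10%: 9.0 against 12.0 ms, 25%.
- p = 20%: 8.0 against 14.0 ms, 42.9%.
- p = 30%: 7.0 against 16.0 ms, 56.2%.

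**Step 4: scale against sampling error.** Standard error of an arm difference = SD × √(2/24). For assumed SDs of 15, 20 and 25 ms it is 4.33, 5.77 and 7.22 ms. A 1 ms loss (Step 2, p = 10%) is small beside these.

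**Step 5: what the other summaries recover.** The by-visit statistics keep the week-24 tracings, but SAP 5.2 does not describe them as within-person change, and their last row pools week 48 with early termination. The abnormal-QTc proportion uses absolute cut-offs, which I take to be in ms: a man going from 390 to 450, or a woman from 400 to 460, rises by 60 and is not counted. The discontinuation summary captures a QTc event only if it was reported as the adverse event that led to stopping.

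**The case against.** The strongest reply is that the harm depends on facts the documents do not supply. Several parts of it stand.

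- A reader might infer that the last ECG of anyone who stops is off drug. The documents do not say so. The visit may fall close to the last dose, and no scheduled off-drug follow-up to week 48 is described.
- A reader might take the 10% yearly loss rate in SAP 1.3 as the diluted share. That is the wrong proxy, because someone truly lost has no early-termination ECG. The 10% row above is only an assumed value of p.
- Replacement of an on-drug tracing mainly concerns those who stop after week 24.
- The protocol's safety background (sections 7 and 11.2) reports no QT signal, and no adverse event led to withdrawal in the pilot. Large reversible changes in people who stop are pure assumption.
- The summary is descriptive, and the week-24 statistics, the any-visit proportion and the discontinuation listing would show much of a real problem. Subtracting baseline from week-24 means gives the mean week-24 change where both ECGs exist.
- Restricting strictly to on-drug tracings could drop early stoppers from the mean altogether.

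The objection does not remove the gap in the rule. It has no on-treatment limit, and none of the other summaries is specified as a within-person change on drug.

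**Conclusion.** The point holds as a minor weakness in how one safety summary is derived. The latest available ECG can be off drug for someone who stops after week 24 and then attends early termination, and it would displace an on-drug tracing. The direction, toward no effect, rests on the assumption that a QTc effect reverses on stopping.

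The size is unknown. Under a uniform, fully reversible effect the proportional loss equals the share whose latest ECG is off drug. It is zero if that share is zero, and greater than the share if those who stop had larger effects. The documents do not support a claim that QTc results will be materially biased, or that tracings from people who stop are off drug as a rule.

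On drug here means within the dosing period. Protocol 9.2.4 holds the dose until clinic at weeks 12, 24 and 48, and ECG timing relative to that dose is not stated.

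**What to change.** In SAP 5.2:
1. Report mean QTc change by arm from baseline to the last on-treatment ECG, with a window after last dose that the sponsor sets and states.
2. Add the maximum post-baseline change per participant.
3. Keep the planned change to the last recorded ECG as a supporting summary, so that early stoppers with no on-drug tracing still appear.
4. Show early-termination ECGs separately from week 48.
5. Reconcile the week-12 EKG, which is in Protocol 9.2.1 and 9.2.2 but not in Appendix 1 or SAP 3.1. It decides whether someone who stops before week 24 can have an on-drug tracing at all.

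A baseline-adjusted arm difference with a 95% confidence interval would be an optional extra.

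The cost is some added derivation and no new assessments. It relies on last-dose dates: diaries and pill counts are collected (Protocol 9.2.4, Appendix 1), but a last-dose date field is not stated, so this needs checking. A few participants will be missing from the on-treatment summary. The maximum tends to rise with the number of ECGs per person, so that number should be shown by arm.

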5.2.1 Columbia-Suicide Severity Rating Scale (C-SSRS)

The C-SSRS captures the occurrence, severity, and frequency of suicide-related thoughts and behaviors during the corresponding assessment period. The scale includes suggested questions to elicit the type of information needed to determine if a suicide-related thought or behavior occurred. The first time the scale is administered in this study, the C-SSRS “Screening/Baseline” version will be used, and the findings will constitute the baseline assessment. The C-SSRS “Since Last Visit” scale will be used for all subsequent assessments.

The number and proportion of subjects with treatment emergent Suicidal ideation or behavior will be reported overall and by study arm.

Treatment emergent suicidal ideation or behavior is defined as a “yes” answer at any time during treatment to any one of the questions in the ten suicidal ideation and behavior categories (Categories 1-10) on the C-SSRS². Self-injurious behavior without suicidal intent, while assessed on the C-SSRS, does not form part of this outcome.

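### The SAP's treatment-emergent suicidality outcome makes no use of the baseline C-SSRS, so unchanged baseline ideation is reported as emergent and worsening cannot be told from persistence

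*SAP*

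**What the plan says.** SAP section 5.2.1 gives the rule for the outcome it labels treatment emergent. A participant is counted on the strength of one yes "answer at any time during treatment to any one of the questions in the ten suicidal ideation and behavior categories". Self-injury without suicidal intent is left out. The planned output is a count and a percentage: "The number and proportion of subjects with treatment emergent Suicidal ideation or behavior will be reported overall and by study arm".

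The same section describes how the instrument is given. The first administration uses the Screening/Baseline form, and "the findings will constitute the baseline assessment". After that the Since Last Visit form applies: that "scale will be used for all subsequent assessments". Protocol section 9.2.2 fixes the timing: the C-SSRS "will be performed at the baseline, 24-week, and 48-week visits". In the Protocol's Appendix 1 the first of these is the week 0 visit, at which study drug is first dispensed.

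SAP section 2.1 lists suicidality rating scale scores as one of five components of Primary Objective 2 (safety and tolerability). SAP section 4.1 defines the Safety Population as randomized participants with at least one dose, whatever their baseline C-SSRS result.

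**The concern.** By its name, a treatment-emergent outcome should hold events that appear or get worse after treatment starts. The rule in SAP 5.2.1 asks only whether a yes was recorded during treatment. A participant with the same ideation before and during treatment meets it. So does one who moves from a mild category to a severe one, and the table cannot separate the two.

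What is at stake is the readability of a named safety component in a small trial. The expected number of cases is low, so one or two carried-over cases can make up much of the reported proportion in an arm. A reader who takes the label at face value would regard them as new.

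**Working it through.** The documents state no C-SSRS rate, threshold or power, so there is no figure to reproduce. The check is first of the text, then an illustration under stated assumptions.

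**1. Does any other text supply a baseline condition?**

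- SAP 5.2.1 has none.
- SAP 5.9 defines baseline and change from baseline in general, but 5.2.1 does not call on it for this outcome.
- SAP 5.2 uses within-subject change for QTc, so the plan makes a baseline comparison elsewhere in safety but not here.
- Protocol 13.1 counts worsening of a pre-existing condition as an adverse event. SAP 5.2.1 goes further and counts unchanged persistence.
- Neither document plans a C-SSRS shift table or a denominator limited to baseline-negative participants.

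**2. Can a baseline-positive participant be in the analysis?** Yes. Protocol 10.1.1 and 10.1.2 contain no C-SSRS criterion. They exclude GDS above 6 and active psychiatric diagnoses that may affect cognition or function, which lowers the chance but does not remove it.

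**3. How the rule classifies four patterns**

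| Baseline | On treatment | SAP 5.2.1 | New or worse |
|---|---|---|---|
| none | category 1 | counted | counted |
| category 1 | category 1 | counted | not counted |
| category 1 | category 4 | counted, same as the row above | counted |
| positive | none | not counted | not counted |

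Rows 2 and 3 show the defect. Row 4 shows its limit: because on-treatment visits use the Since Last Visit form, ideation that lies wholly in the past is not counted.

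**4. Chance imbalance.** SAP 3.1 gives 47 randomized at 1:1. Assume a 24/23 split and two carried-over cases.

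- Both in the arm of 24: 2/24 = 8.3% against 0%. Both in the arm of 23: 2/23 = 8.7% against 0%.
- Chance that both fall in the same arm: (276 + 253)/1081 = 49%, where 276, 253 and 1081 are the numbers of pairs among 24, 23 and 47.

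**5. Inflation, over a range.** Let b be the share positive at baseline, r the share of those with a yes again on treatment, and e the new-onset rate among baseline negatives. All three are assumptions.

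- Rate under SAP 5.2.1 = b·r + (1 − b)·e
- New-onset rate = (1 − b)·e (this leaves out worsening among baseline positives)
- Carried-over share of counted cases = b·r / [b·r + (1 − b)·e]

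Take b = 2% to 10%, r = 30% to 80%, e = 2% to 5%, N = 47:

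- Expected cases under SAP 5.2.1 run from 47 × 0.0256 = 1.2 to 47 × 0.125 = 5.9, both arms together.
- Expected new-onset cases run from 47 × 0.018 = 0.85 to 47 × 0.049 = 2.3.
- The carried-over share runs from 0.006/0.055 = 11% to 0.080/0.098 = 82%.
- The chance of at least one baseline-positive participant, 1 − (1 − b)^47, is 61%, 91% and 99% for b = 2%, 5% and 10%.

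**6. Is the arm comparison biased?** Assume b = 10% in each arm, r = 100%, and new-onset rates of 15% and 5%.

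- SAP 5.2.1: 0.10 + 0.90 × 0.15 = 23.5% and 0.10 + 0.90 × 0.05 = 14.5%; difference 9.0 points, ratio 1.6.
- New onset only: 0.90 × 0.15 = 13.5% and 0.90 × 0.05 = 4.5%; difference 9.0 points, ratio 3.

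With equal carry-over the difference is unchanged. Only the levels and the ratio move, and the SAP plans no ratio.

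**The case against.** The strongest reply is that this is a label on a descriptive count. Several parts of that reply stand.

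- A reader might infer that pre-existing ideation is being attributed to the drug. The documents do not support that. Treatment emergent is a statement about timing, and SAP 5.2.1 makes no causal claim. Relatedness is judged event by event under Protocol 13.1.2 and tabulated for adverse events under SAP 5.2.
- A reader might infer a bias against nicotinamide, or a rule that hides a true effect. Randomization against placebo makes carried-over cases equal between arms in expectation, and step 6 shows the arm difference is then preserved.
- The split of 8.3% against 0% is weak evidence of anything. The SAP plans no test of this outcome; on 2/24 against 0/23 a two-sided Fisher test would give p of about 0.49. Two truly new cases would be just as fragile.
- Over-counting is a defensible direction for a safety screen. New or worsened suicidality recorded as an adverse event would also appear in the TEAE tables.
- The definition cites a C-SSRS scoring guide (SAP reference 2) that was not available for this review. Whether it adds a baseline rule cannot be checked.

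None of this supplies the missing condition. As written, the SAP's rule cannot separate new or worse from unchanged, and its name says that it does.

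**Conclusion.** The point holds as a mismatch between name and rule in a component of Primary Objective 2. Unchanged ideation that is reported again on treatment is counted as emergent, and worsening is indistinguishable from persistence. The consequence is an inflated proportion in both arms, plus chance imbalance that matters because only 47 were randomized. The documents do not allow the size to be fixed. Under the assumed ranges, between 11% and 82% of counted cases would already have been positive at baseline. If no participant was positive at baseline, the two definitions give the same result.

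The reach is limited to one descriptive safety outcome. The primary efficacy analysis, the sample size and the data collection are not affected.

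**What to change.** In SAP 5.2.1, define treatment-emergent suicidal ideation or behavior as a post-baseline C-SSRS category that is absent at baseline or more severe than the worst category recorded at baseline. The same sentence should state the severity order used, the look-back period of the baseline form that serves as the comparator, and whether a milder category first recorded on treatment counts. SAP 5.2.1 does not settle these.

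Keep the present count, renamed any on-treatment suicidal ideation or behavior, and report it by arm and by baseline status. A shift table from baseline to worst on-treatment category, by arm, would do this.

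The cost is one sentence and one table. The baseline, week 24 and week 48 assessments are already in the schedule, so no new data are needed.

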5.3 Analysis of Secondary Efficacy Outcomes

Mean differences in the within subject change in CSF p-tau181, CSF total tau, CSF A β 40, CSF A β 42, ADAS-cog13, ADCS-ADL-MCI, and CDR-SB will be tested between treatment arms, as described below. To control the familywise type I error rate at level 0.05 (two-sided) within each objective, the Holm-Bonferroni closed testing procedure will be utilized. Secondary analyses will be conducted on the mITT population.

5.3.1 Secondary Objective 1

The efficacy of nicotinamide will be assessed by the mean within-participant changes from baseline to week 48, compared between the treatment group and the placebo group, on the following CSF biomarker measures:

- amyloid beta (A β 42),

- amyloid beta (A β 40),
- phosphorylated tau (p-tau₁₈₁),
- total tau (t-tau),
- the ratio of total tau/A β 40,
- the ratio of total tau/ A β 42

Analyses will be the same as the primary efficacy outcome analysis. The Holm-Bonferroni closed testing procedure will be utilized to control the family-wise error rate at the 5% level across the 6 hypothesis tests.

5.3.2 Secondary Objective 2 Determine if daily treatment with high-dose nicotinamide in individuals with mild AD dementia or MCI due to AD reduces the rate of cognitive decline, as assessed by ADAS-Cog 13

5.3.3 Secondary Objective 3

Alzheimer's Disease Cooperative Study-Activities of Daily Living - MCI (ADCS-ADL-MCI)

The ADCS-ADL-MCI is a measure of patient functional performance in AD and MCI trials. The informant-based questionnaire assesses conduct of basic and instrumental ADLs. A total of 24 ADLs are evaluated. Scores range from 0 to 53, with higher scores representing more maintained function.

CDR-Sum of Boxes

The CDR uses patient and informant interviews to assess memory, orientation, judgment and problem solving, community affairs, home and hobbies, and self-care. The CDR can provide a global score of 0, 0.5, 1.0, 2.0, or 3.0 relating to not demented, very mild dementia, mild dementia, moderate dementia, and severe dementia, respectively. Alternatively, a sum of the boxes can be assessed, providing a wider range and greater sensitivity to change.

The within-participant change in each of these three measures (ADAS-Cog 13 ADCS-ADL-MCI and CDR) will be evaluated with a longitudinal mixed effects model with repeated measures. Terms in the model will be: age, baseline score, treatment, time defined categorically as visit, and time by treatment interaction.

A random effect will be included for participant. The within-participant covariance matrix will be unstructured. If the model does not converge a compound symmetry covariance matrix will be used. If the model still does not converge, the ANCOVA approach of the primary analysis will be used, using the last available measurement for each subject. Each endpoint will be tested using model-adjusted least squares means at the week 48 visit. A point estimate, standard error and two-sided 95% Wald confidence interval and a p-value will be presented for the difference between arms at 48 weeks. The Holm-Bonferroni closed testing procedure will be utilized to control the family-wise error rate at the 5% level across the 3 hypothesis tests.

Point estimates, standard errors and two-sided 95% confidence intervals for the mean within patient change at each time point will be presented by arm, as descriptive statistics unadjusted for multiple confidence intervals.

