3 STUDY DESIGN

3.1 Synopsis of Study Design

Forty-seven participants were randomized to 1500 mg BID nicotinamide or matched placebo at a 1:1 ratio, stratified by site, diagnostic category (MCI or dementia), and APOE genotype ($\epsilon 4$ carriers, $\epsilon 4$ non-carriers).

There was a screening period of up to 60 days, during which each participant completed 3 screening visits.

The ADAS-Cog 13, ADCS-ADL-MCI and CDR-SB were collected at 3 timepoints: baseline, week 24, and week 48. The MMSE was collected at screening visit 1, baseline, week 24, and week 48. the Free and Cued Selective Reminding Task (FCSRT) was only done at screening visit 1.

Lumbar punctures and MRI scans were performed at screening and week 48. Safety measures including the C-SSRS, EKG, and safety laboratories were collected at screening or baseline, week 24, and week 48. Vital signs, blood collection for biomarker banking, physical exams, and neurological exams were done at screening or baseline, week 24, week 36, and week 48. Concomitant medications and adverse events were collected at every visit.

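### If a clinical mixed model falls back to compound symmetry, the week-48 standard error rests on a variance pooled over weeks 24 and 48, and is too small if the residual variance is larger at week 48

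*SAP*

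**What the plan says.** SAP 3.1 states that the clinical scales "were collected at 3 timepoints: baseline, week 24, and week 48". For the model, SAP 5.3.3 states: "Terms in the model will be: age, baseline score, treatment, time defined categorically as visit, and time by treatment interaction". Baseline score is a covariate, so the responses are the two post-baseline visits, weeks 24 and 48.

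The covariance is specified in three steps:

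- **First choice.** "A random effect will be included for participant", and "The within-participant covariance matrix will be unstructured".
- **First fallback.** "If the model does not converge a compound symmetry covariance matrix will be used".
- **Second fallback.** "If the model still does not converge, the ANCOVA approach of the primary analysis will be used", applied to each participant's last available value.

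Inference is at a single visit: "Each endpoint will be tested using model-adjusted least squares means at the week 48 visit". It uses a two-sided 95% Wald interval and p-value, with Holm-Bonferroni at 5% across the three clinical tests. Huber-White variance is specified in SAP 5.1 for the primary ANCOVA. The analyses modelled on that ANCOVA inherit it: the CSF secondaries, the MRI measures and the second fallback above. The SAP specifies no robust variance for the mixed model, and neither document gives a week-24 or week-48 standard deviation for any clinical scale.

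**The concern.** Compound symmetry without further qualification means one variance and one correlation. The standard error of the week-48 contrast is then built from a variance averaged over weeks 24 and 48. If the two visits have the same residual variance, nothing is lost. If week 48 is more variable, the average understates it, the interval is too narrow and the test rejects too often. If week 48 is less variable, the test is conservative.

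Larger variance at week 48 is plausible. The secondary objectives concern rates of decline, and if participants decline at different rates, their scores conditional on baseline diverge as time passes. This is an argument from the kind of outcome; the documents contain no figure for it.

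The p-value and interval of any clinical endpoint that reaches this fallback are at stake, and so is the Holm procedure that takes that p-value as input. The fallback gains little in return: with two visits it estimates two covariance parameters instead of three.

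**Working it through.** **Inputs from the documents.** Two post-baseline visits (SAP 3.1); 47 participants randomized 1:1 (SAP 3.1); 10% loss to follow-up per year (SAP 1.3); two-sided 95% Wald test at week 48 and Holm across three tests (SAP 5.3.3).

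**Assumed input.** R, the week-48 residual variance divided by the week-24 residual variance, both after adjustment for baseline score and age. The documents do not give it.

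**1. Nominal level.** With R = 1 the two-sided test at 1.96 has level 5.0%, as the SAP intends.

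**2. Standard error under compound symmetry.** With complete data the model uses (v24 + v48)/2 where v48 is needed. The ratio of reported to true standard error is f = sqrt((1 + 1/R)/2), and the actual level is 2 × (1 − Φ(1.96 × f)).

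| R | f | 1.96 × f | Actual level of a nominal 5% test |
|---|---|---|---|
| 0.8 | 1.061 | 2.079 | 3.8% |
| 1.0 | 1.000 | 1.960 | 5.0% |
| 1.2 | 0.957 | 1.877 | 6.1% |
| 1.5 | 0.913 | 1.789 | 7.4% |
| 2.0 | 0.866 | 1.697 | 9.0% |

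R = 2.0 is the case where variance is proportional to time since baseline.

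**3. Simulation check.** REML fits under no treatment effect: 47 participants split 24:23, 10% missing at week 48, age and baseline as covariates, correlation 0.6 (also 0.4 and 0.8 at R = 2.0), 1,500 runs per setting. Monte Carlo error is about 0.6 to 0.8 points.

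| R (SD ratio) | Formula | Simulated compound symmetry, Wald |
|---|---|---|
| 1.00 (1.0) | 5.0% | 5.6% |
| 1.44 (1.2) | 7.1% | 7.7% |
| 1.69 (1.3) | 8.0% | 8.6% |
| 2.00 (1.414) | 9.0% | 8.4% to 9.7% |
| 2.25 (1.5) | 9.6% | 9.5% |

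A second simulation (44 participants, correlation 0.6 to 0.8, 3,000 runs per setting) gave 5.7% at R = 1.0, 8.2% at 1.5 and 9.8% to 10.1% at 2.0. Simulated levels run up to about one point above the formula. Part of that is the use of a normal reference in a small sample and has nothing to do with compound symmetry: the unstructured model in the second simulation ran at 5.7% to 6.3%.

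**4. Through Holm.** At the first step (0.05/3 = 1.67%), the formula gives 2.9% at R = 1.5 and 3.8% at R = 2.0. Suppose all three nulls are true and one endpoint falls back. The union bound on the familywise error is 2 × 1.67% + 2.9% = 6.2%, or 2 × 1.67% + 3.8% = 7.1%. If all three fall back with R = 2.0 and the tests were independent, it is 1 − (1 − 0.0381)³ = 11.0%.

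**5. How the fallback is reached.** Two visits have three variance-covariance elements: two variances and one covariance. An unstructured matrix uses three parameters. The participant random effect adds a fourth, so the first-choice model has four parameters for three elements and one is not identified. Without the random effect, REML fits of the unstructured model (47 participants, 10% missing at week 48, correlation 0.4 to 0.9, R from 1 to 2) had no failures in 1,000 runs.

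**The case against.** The strongest objection is that this branch may never be used. An unstructured matrix for two visits fits easily alone, so failure would most likely come from the redundant random effect. That effect is just as redundant with compound symmetry (three parameters for two elements). If it stops the first model, it may stop the second too, and the analysis then passes to the ANCOVA with Huber-White variance, where no visit variances are pooled. This stands. It makes the harm conditional on an event whose probability cannot be given, but it does not remove a prespecified step that has the weakness.

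The second objection is that variance growth is assumed. Neither document reports it, and the relevant quantity is residual variance after adjustment for baseline and age, which can differ from the spread of raw scores. This also stands. Growth of 10% to 20% in variance gives roughly 6%, and a smaller week-48 variance makes the test conservative.

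A reader might infer that the clinical tests run at 8% to 10%, or that the familywise level for Secondary Objectives 2 and 3 is lost. The documents do not support either. The 8% to 10% range needs a variance ratio of about 1.5 to 2 and includes small-sample Wald inflation that an unstructured fit shows as well. The familywise figure depends on how many endpoints fall back, and nothing says that all three will.

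**Conclusion.** The fallback has a real but minor weakness. If a clinical endpoint's model reaches compound symmetry, and if its residual variance is larger at week 48 than at week 24, the week-48 standard error is too small: by about 9% at a variance ratio of 1.5 and 13% at 2.0. The nominal 5% test then runs at about 7.4% or 9.0%, plus up to about one point from the small-sample Wald reference. At ratios of 0.8 to 1.2 the level is 3.8% to 6.1%.

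This rests on reading compound symmetry in its usual homogeneous sense. A version with separate visit variances would have the same three parameters as the unstructured matrix for two visits, and so would not be a fallback at all. It also rests on an assumed variance ratio. The point does not touch the primary p-tau231 analysis, the CSF secondaries or the MRI measures, and it does not show that any clinical result will be wrong.

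**What to change.** In SAP 5.3.3, delete the participant random effect and fit the unstructured residual covariance for weeks 24 and 48. This removes the likeliest cause of non-convergence. In the 47-participant simulation, at SD ratios of 1.0 to 1.5, this model held the Wald test at 4.4% to 5.6%.

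If compound symmetry is kept as a fallback, state that the week-48 standard error comes from a participant-clustered sandwich estimator with a small-sample correction and a t reference. Over the same range that gave 3.6% to 4.7%.

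The cost is one sentence in the SAP and one option in the model call, with no extra data or participants. Intervals may be slightly wider if the fallback is used. The change should be made before unblinding, so that the choice of standard error cannot depend on the result.
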